#### **4.7.4 Vaccination Against COVID-19**

There are no clinical data available to assess the interaction (if any) of MEDI3506 with any COVID-19 vaccine.

The sponsor accepts that vaccination against COVID-19, when and where it is available, and when subjects are eligible according to the applicable guidelines, is in the subject's best interest. Consequently, vaccination during the study is, in general, permitted and any delays in receiving the vaccination due to study participation should be minimized.

To help ensure the interpretability of the safety data, receipt of the COVID-19 vaccine (either the first or subsequent dose) is prohibited within 28 days before randomization or within 7 days before or after any dose of MEDI3506/placebo. Receipt of, at least, the first dose of a COVID-19 vaccine more than 28 days before randomization, without significantly delaying enrollment, is preferred but may not be possible, eg, not locally available at the time, subject not eligible at the time, express subject decision not to be vaccinated. Otherwise, vaccination may be performed at any time outside the prohibited 7-day window before or after any dose of MEDI3506/placebo. If the (approximate) date of a subsequent dose of COVID-19 vaccination is known, then enrollment of the subject should be timed so that the dose is not within 28 days before the scheduled randomization. If this date is not known, then enrollment into the study should not be delayed. If an enrolled subject does (unexpectedly) receive the COVID-19 vaccine within 28 days before the scheduled randomization, the site should contact the AstraZeneca Study Physician for advice on how the situation should be managed.

If and when a subject receives a COVID-19 vaccination, the following information will be recorded in the eCRF as a concomitant medication: the date, dose, brand name, site of administration, and lot number (if known) of each vaccine dose (eg, 10 Feb 2021; first dose; Pfizer-BioNTech COVID-19 Vaccine; left Deltoid; Lot xxx).

Any AEs suspected to be due to the vaccination should be captured in the AE form including the causality assessment related to COVID-19 vaccine.

### **4.8 Statistical Evaluation**

#### **4.8.1 General Considerations**

Tabular summaries will be presented by treatment group, with the 4 volume-matched placebo groups combined. Categorical data will be summarized by the number and percentage of

subjects in each category. Continuous variables will be summarized by descriptive statistics. Study populations are described in Table 11. Additional details of statistical analyses will be described in the statistical analysis plan (SAP).

**Table 11 Study Populations**

Population	Description
Enrolled	All subjects who sign the informed consent form.
Full Analysis Population	All subjects who are randomized and receive any study drug. Subjects are evaluated according to the treatment assigned at randomization. The Full Analysis Population will be used for all analyses of demographic baseline characteristics and efficacy data.
Per Protocol Population	A subset of the Full Analysis Population consisting of all subjects who receive the additional treatment with dapagliflozin post Week 12 and do not violate the terms of the protocol in a way that may affect the primary efficacy endpoint significantly. All decisions to exclude subjects from the per protocol analysis set will be made and documented prior to the unblinding of the study.
Safety Analysis Population	All subjects who are randomized and receive any study drug. Subjects are evaluated according to the actual treatment they received. The Safety Analysis set will be used for all safety analyses.
PK Population	All subjects in the Full Analysis Population who have at least one detectable MEDI3506 serum concentration measurement posttreatment. The PK Analysis set will be used for all PK analyses.

PK = pharmacokinetic(s).

## 4.8.2 Sample Size

A sample size of 565 subjects randomized using a 95:95:95:140:140 ratio to receive either 30, 60 mg, 120 mg, or 300 mg MEDI3506 or placebo will give approximately 85:85:85:125:125 evaluable subjects per group. This will provide at least 85% power for the 300 mg arm and 80% power for the 30, 60, and 120 mg arms to detect a 30% reduction in change from baseline to Day 169 (Week 24) in UACR between each MEDI3506 treatment group and placebo group (or placebo/ MEDI3506 ratio of 1.429) with a one-sided alpha of 0.05 without multiplicity adjustment, assuming a coefficient of variation of 1.31 or standard deviation of 1.0 in log scale.

## 4.8.3 Efficacy

### 4.8.3.1 Primary Efficacy Analysis

The primary efficacy endpoint for this study is change from baseline to Day 169 (Week 24) in UACR compared to placebo and will be analyzed based on the Per Protocol Population. For the intercurrent events, if a subject is lost to follow-up, discontinues treatment due to AE or lack of efficacy, or uses prohibited medication, the UACR data are treated as missing after the event and no imputation is performed. As UACR is assumed to follow a log-normal

distribution, it will be log-transformed for statistical analysis purposes. The primary analysis will use a mixed model repeated measures (MMRM) analysis of change from baseline in UACR without multiplicity adjustment. The model will adjust for fixed categorical effects of treatment, visit, and treatment-by-visit interaction, randomization stratification factors, and the continuous covariates of baseline log UACR and baseline log UACR-by-visit interaction. UACR will be log-transformed before entering the data in the MMRM analysis to alleviate the skewness of the data. Randomization stratification factors are with SGLT2i background or not, in Japan or rest of world.

To allow generality for the covariance structure for the repeated measures, the variance-covariance matrix will be assumed to be unstructured ie, purely data dependent. If the unstructured variance-covariance matrix will not fit, then suitable alternatives will be considered with details provided in the SAP. In this MMRM model, all subjects and all data points will be included. No subjects will be excluded because of missing data, and no imputation will be done for missing data. Additionally, there will be no adjustment for multiplicity.

Additionally, the primary efficacy endpoint will also be analyzed using an analysis of covariance adjusting for treatment, randomization stratification factors, and baseline log UACR with last-observation-carried-forward (LOCF) imputation for missing postbaseline measurements.

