### 3.1.2 Treatment Regimen

CCI

- Group 1: MEDI3506 30 mg (0.2 mL), n = 95
- Group 2: MEDI3506 60 mg (0.4 mL), n = 95
- Group 3: MEDI3506 120 mg (0.8 mL), n = 95
- Group 4: MEDI3506 300 mg (2 mL), n = 140
- Group 5: Placebo (0.2 mL), n = 32
- Group 6: Placebo (0.4 mL), n = 32
- Group 7: Placebo (0.8 mL), n = 32
- Group 8: Placebo (2 mL), n = 44

All subjects will also receive daily oral tablets of 10 mg dapagliflozin starting on Day 85 until Day 168. Subjects already taking an SGLT2i will be rolled over to 10 mg dapagliflozin.

Dapagliflozin should be taken in the morning with or without food.

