### **4.6 Treatment Assignment and Blinding**

#### **4.6.1 Methods for Assigning Treatment Groups**

An IXRS will be used for randomization to a treatment group and assignment of blinded investigational product kit numbers. A subject is considered randomized into the study when the investigator notifies the IXRS that the subject meets eligibility criteria and the IXRS provides the assignment of blinded investigational product kit numbers to the subject.

Subjects will be stratified at the time of randomization in order to ensure approximate balance between treatment groups within each sub-population.

- Stratum 1: Subjects without SGLT2i background outside Japan
- Stratum 2: Subjects with SGLT2i background outside Japan
- Stratum 3: Subjects without SGLT2i background in Japan
- Stratum 4: Subjects with SGLT2i background in Japan

Subjects will be randomized to receive 30, 60, 120, or 300 mg MEDI3506 (95, 95, 95, and 140 subjects, respectively) CCI placebo (32, 32, 32, and 44 subjects, respectively) by an IXRS system.

IXRS will also allocate 2 bottles of dapagliflozin (35 tablets each) at Visit 6 and 1 bottle of dapagliflozin (35 tablets) at Visit 7 to eligible subjects that will be used to cover the need of daily administration between two visits of MEDI3506/placebo administration. This will ensure that the patient has sufficient stock of dapagliflozin if a visit is delayed. If there is any issue with one of the bottles (eg, lost or damaged), the patient can receive a replacement at any visit (Visit 7 or Visit 8); kit replacement option is available in IXRS.

The procedure for using IXRS is as follows:

- The investigator or designee contacts the IXRS and provides the SID number and subject's baseline characteristic(s) used to verify that it is the same subject
- The correct amount of kits of MEDI3506 and/or placebo will be assigned to the subject
- Confirmation of kit assignment is sent to the unblinded investigational product manager who prepares the investigational product to be dispensed to the subject per the response system and records the appropriate information in the investigational product accountability log
- Blinded study personnel will receive a notification containing a dose tracking number, that will not disclose how many kits are assigned to the subject.

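### The primary MMRM holds the SGLT2i-background effect constant across visits although the design shifts it after Day 85, so the Day 169 variance is slightly overstated

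*Protocol*

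**What the plan says.** Section 4.8.3.1 lists the fixed effects of the primary model: "fixed categorical effects of treatment, visit, and treatment-by-visit interaction, randomization stratification factors", then baseline log UACR and its interaction with visit. The stratification factors named there are SGLT2i background (yes/no) and region (Japan or rest of world). No stratum-by-visit term appears, and the synopsis gives the same list. The covariance is unstructured.

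Section 4.6.1 randomises within strata formed from these two factors, beginning with "Stratum 1: Subjects without SGLT2i background outside Japan".

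Section 3.1.2 gives everyone dapagliflozin from Day 85 and adds: "Subjects already taking an SGLT2i will be rolled over to 10 mg dapagliflozin". Section 4.7.3 lets prior users keep their SGLT2i until Day 85. Section 1.8.2 expects dapagliflozin to lower albuminuria further.

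Section 4.8.2 plans "at least 85% power for the 300 mg arm and 80% power for the 30, 60, and 120 mg arms", "with a one-sided alpha of 0.05 without multiplicity adjustment", and "assuming a coefficient of variation of 1.31 or standard deviation of 1.0 in log scale"; the planned enrolment "will give approximately 85:85:85:125:125 evaluable subjects per group".

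**The concern.** Up to Day 85 the two background groups differ in whether they take an SGLT2i at all. After Day 85 both take dapagliflozin. Users have had the class effect in their UACR since baseline; non-users acquire it only after Day 85. On the protocol's own expectation, change from baseline in non-users should drop at Days 113, 141 and 169, with no matching drop in users.

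A single background coefficient cannot follow that. It settles between its pre-switch and post-switch values, and the remainder goes into the residual at every visit, including Day 169, where the primary contrast is read. The model lets the baseline UACR effect vary by visit, but not the one covariate whose effect the design itself changes mid-trial. At stake is a little precision and, under a particular pattern of losses, a small shift in the estimate.

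**Working it through.** **1. The plan's own power.** Inputs from section 4.8.2: effect ln(1/0.7) = 0.3567, SD 1.0 (CV 1.31 gives 0.9996), one-sided alpha 0.05.
- 300 mg, 125 v 125: 0.3567/√(2/125) = 2.820; Φ(2.820 − 1.645) = 88.0%.
- Lower doses, 85 v 125: 0.3567/√(1/85 + 1/125) = 2.537; Φ(2.537 − 1.645) = 81.4%.

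Both agree with the stated power.

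**2. What the constant coefficient estimates.** There are six post-baseline visits (Days 29, 57, 85, 113, 141, 169). Day 85 counts as pre-switch because its urine samples come from that morning and the two preceding days. Let e be the dapagliflozin effect in log units, b = e·(0,0,0,1,1,1), S the visit covariance and p the share of users. With complete data and balanced strata, the coefficient converges to

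g = 1′S⁻¹b / 1′S⁻¹1.

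Under AR(1) or compound symmetry with equal variances, three visits lie on each side of the switch, so g = e/2.

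**3. Variance at Day 169.** Relative inflation = p(1−p)(e−g)²/S₆₆. With g = e/2:

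| p | e | SD 1.0 | SD 0.7 |
|---|---|---|---|
| 0.30 | 0.30 | 0.21 × 0.15² = 0.47% | 0.96% |
| 0.50 | 0.30 | 0.25 × 0.15² = 0.56% | 1.15% |
| 0.30 | 0.43 | 0.21 × 0.215² = 0.97% | 1.98% |
| 0.50 | 0.43 | 0.25 × 0.215² = 1.16% | 2.36% |

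The values of p, e, the AR(0.7) correlation and SD 0.7 are assumptions. An e of 0.30 to 0.43 log is a 26% to 35% reduction.

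**4. Check by simulation** (505 subjects, complete data, balanced strata, 3,000 runs; 30% users, 30% dapagliflozin effect, AR, SD 1.0). The mean model SE was 0.1270 with the constant term and 0.1266 with the by-visit term, a ratio of 1.003. Bias (0.0012) and empirical SE (0.1238) were the same in both models. One-sided type I error was 4.7% against 4.8%.

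**5. Wider range.** If variance also grows over visits, g falls to about 0.18e and more of the shift is left in the Day 169 residual. With SD 0.7 the simulated SE ratio was 1.018 (30% users, 30% effect) and 1.044 (50% users, 40% effect), with type I error 4.3% and 3.9%. At the other end (15% users, 20% effect, SD 1.0, equal variances) the ratio is 1.0008.

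**6. Power.** If the planning SD of 1.0 is the residual SD under the constant-term model, removing 1.16% of variance gives Φ(2.537 × √1.0116 − 1.645) = 81.8% and Φ(2.820 × √1.0116 − 1.645) = 88.3%, a gain of at most about 0.4 points. If instead 1.0 is the correctly specified SD, dividing by √1.0116 gives 81.0% and 87.7%. Both readings meet the stated power.

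**7. Losses after Day 85** (constant-term minus by-visit estimate at Day 169, log units).
- Equal 10% in every cell: 0.000.
- 25% of non-users and 10% of users, the same in both arms: bias 0.001 (Monte Carlo SE 0.009), so none detectable.
- Placebo 10%/10%; active 20% of non-users, 5% of users: 0.009 to 0.012.
- Opposed patterns (placebo 5% of non-users, 20% of users; active 25% and 5%): 0.022 to 0.030, which is 6% to 8% of 0.357.

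These have every loss occurring straight after Day 85. When I spread the losses evenly over the three later visits, the shifts roughly halved.

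**The case against.** The strongest reply is that nothing turns on this. In the base case the SE differs by 0.3%, the estimate is unaffected, the error is on the conservative side, and the planned power holds. That stands, and it fixes the weight of the point.

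The section also specifies an ANCOVA at Day 169 whose stratum coefficient belongs to that endpoint alone. That is a fair partial check. But it is a supplementary analysis, and its LOCF carries pre-switch values forward, so it does not repair the primary model.

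The SAP could add the term. It could, but the protocol already lists which covariates get visit interactions and leaves this one out.

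The share of users, the effect size and the covariance are not in the protocol. This is correct. With 10% to 15% users at SD 1.0, variance inflation is only 0.2% to 0.6%.

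A reader might infer more than the protocol supports, in three ways:
- That losses differing by stratum alone bias the estimate. They do not, because the strata then stay balanced across arms; the losses must differ by arm as well.
- That the power gain approaches a full point. That pairs the inflation found at SD 0.7 with the power at SD 1.0. At SD 0.7 power for 85 v 125 is already about 97%, and the gain is about 0.1 to 0.2 points.
- That every secondary UACR model needs the term. The Day 85 to Day 169 change has only post-switch outcome visits, and a Day 85 model confined to visits up to Day 85 has only pre-switch ones.

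**Conclusion.** The point holds as a minor one. The listed model cannot represent a shift that the design builds in, so the Day 169 variance is overstated by about 0.5% to 1.2% at SD 1.0 and 1.0% to 2.4% at SD 0.7. This rests on the assumptions in steps 2 and 3 of the working. Growing variance makes it larger: at SD 1.0 with 50% users and a 40% effect the SE rises by about 2.2%. If 1.0 is then the correctly specified SD, lower-dose power sits at about 80%.

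The treatment estimate is unbiased while strata are balanced across arms. A small shift needs losses after Day 85 that differ by both arm and stratum. The protocol leaves room for this, since the primary analysis is Per Protocol and sets UACR to missing after certain events. It gives no reason to expect that pattern.

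**What to change.** Add SGLT2i-background-by-visit to the fixed effects of the primary MMRM in section 4.8.3.1 and the synopsis, and carry it into the SAP. Do the same in any secondary repeated-measures UACR model that spans visits both before and after Day 85; models confined to one side of the switch do not need it on this ground.

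The cost is five degrees of freedom (six visit-specific coefficients in place of one) among about 505 evaluable subjects. No data collection, visit or sample-size change is needed. It should be written in before unblinding, because adding it afterwards would be post hoc.

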#### 4.1.2 Inclusion Criteria

Subjects must meet all of the following criteria:

- 1 Adult men or women  $\geq 18$  years of age at Visit 1.
- 2 Written informed consent and any locally required authorization (eg, data privacy) obtained from the subject prior to performing any protocol-related procedures, including screening evaluations.
- 3 DKD defined as
  - (a) diagnosis of T2DM and
  - (b) eGFR 25-75 mL/min/1.73 m^2 based on Chronic Kidney Disease Epidemiology Collaboration (CKD-EPI) equation a and
  - (c) UACR defined as 100-3000 mg albumin/g creatinine based on the mean of 3 sequential first morning void midstream urine samples at Visit 2.
- 4 BP  $\leq 150/100$  mmHg at Visit 1 and Visit 3.
- 5 Stable dose of ACEi or ARB for at least 6 weeks prior to Visit 1 and throughout the screening period with ACEi and ARB dosing according to local guidelines. Subjects who have been deemed unable to tolerate ACEi or ARB therapy due to allergy or complications may be enrolled. Minor dose adjustment within 2 weeks before Visit 1 is acceptable (see Section 4.7.2).

- 6 For subjects on any additional antihypertensive medication (including diuretic therapy), doses must be stable for at least 6 weeks prior to Visit 1 and throughout the screening period.
- 7 For subjects on SGLT2i treatment prior to enrollment, doses must be stable for at least 4 weeks prior to Visit 3. Existing SGLT2i treatment will be stopped and switched to 10 mg dapagliflozin on Day 85.
- 8 Up-to-date influenza and pneumococcal pneumonia vaccinations (subject-reported) according to local recommendations, at least 28 days prior to Visit 3 OR confirmation of off-season intent to get vaccinated. Patients screened outside of the influenza season (including those who were not vaccinated in the previous season) are eligible for randomization provided that the vaccination is planned once the influenza vaccine for the next season becomes available. For such patients, investigators are asked to confirm the patient's intent to get vaccinated for the next season. Patients who do not plan to get vaccinated against influenza should not be randomized.
- 9 Contraceptive use by men or women should be consistent with local regulations regarding the methods of contraception for those participating in clinical studies.
  - (a) Male subjects:

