**Table 6 Schedule of Treatment Period Study Procedures**

Study Period	Treatment Period							Early D/c Visit
Visit Number	V3	V4	V5	V6	V7	V8	V9	
Procedure / Study Day	Day 1	Day 29 (± 5 days)	Day 57 (± 5 days)	Day 85 (± 5 days)	Day 113 (± 5 days)	Day 141 (± 5 days)	Day 169 (± 5 days)	

- a Including focused cardiac exam (Section 4.3.2.2).
- b For the first 2 doses of MEDI3506 or placebo, patients are to remain at the site for  $\geq 2$  hours or until stable, whichever is later. In addition, vital signs will be taken before and immediately after administration of MEDI3506 or placebo, and at 30 minutes ( $\pm 5$  minutes) as well as 120 minutes ( $\pm 10$  minutes) thereafter or until stable, whichever is later. Following the observation period, subject discharge will be at the discretion of the investigator. For all other dosing visits, vital signs will be collected 30 minutes ( $\pm 5$  minutes) after administration of MEDI3506 or placebo or when stable.
- c May be performed independently of other Visit 9 procedures within the visit window.
- d PK samples on MEDI3506/placebo dosing days will be collected pre-dose of MEDI3506/placebo administration.
- e Dapagliflozin PK samples will be collected at the following time points relative to dapagliflozin administration: Day 141 (predose and 2 h postdose) and Day 169 on study visit. Patients will be reminded to take dapagliflozin on site visits during dapagliflozin administration time (Day 85 to Day 168/Visit 6 to Visit 8).

- g If consent obtained.
- h After randomization. If, for any reason, the sample is not drawn pre-dose on Visit 3 (Day 1), it may be taken at any visit until the final follow-up visit/Early Discontinuation Visit.
- i Subjects collect 3 consecutive first morning void midstream urine samples (ideally day of visit and preceding 2 days [refrigerated overnight]) which are returned on the day of visit.
- j In the event that a dose cannot be administered within the window of the scheduled dosing date, the dose may be administered outside of the dosing window as long as it is at least 14 days prior to the next dose and recorded as a protocol deviation.
- k Subjects enrolled that have reached the Day 85 visit prior to Amendment 2 approval should continue in the study without the addition of dapagliflozin to their dosing regimen.

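### Two three-void UACR collections precede the first dose, but the primary models name one baseline term; using both would give an optional, assumption-dependent gain in precision

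*Protocol*

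**What the plan says.** **First collection.** Inclusion criterion 3(c) in Protocol section 4.1.2 sets the UACR eligibility range of 100 to 3000 mg/g "based on the mean of 3 sequential first morning void midstream urine samples at Visit 2". A footnote to Table 5 lets this collection be repeated once during screening.

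**Second collection.** The UACR row of Table 6 is marked at Visit 3 (Day 1), and its footnote again asks for three voids: "Subjects collect 3 consecutive first morning void midstream urine samples". First-morning voids brought to that visit precede the first injection.

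**Models.** Section 4.8.3.1 lists the covariates of the primary MMRM. The only UACR terms are "baseline log UACR and baseline log UACR-by-visit interaction". The LOCF ANCOVA has the same single UACR covariate. Section 4.8.3.2 analyses change to Day 85 in a similar way. Section 4.8.1 leaves further analysis detail to the SAP.

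**Power.** Section 4.8.2 claims "at least 85% power for the 300 mg arm and 80% power for the 30, 60, and 120 mg arms". The effect sought is a UACR 30% lower than on placebo at Week 24, each dose being tested one-sided at the 5% level with no correction for the number of doses. The variability input reads "assuming a coefficient of variation of 1.31 or standard deviation of 1.0 in log scale".

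**The concern.** UACR varies within a person from day to day, so one three-void value measures a subject's starting level with error. A covariate measured with error removes less variance than the true level would. A second measurement taken before randomisation recovers part of the difference, and here it is already scheduled for every randomised subject. If the single baseline term is one of the two sets, the other goes unused in the primary comparison and in the Day 85 comparison. What is at stake is precision, not validity. The 30, 60 and 120 mg arms have the least room above their target.

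**Working it through.** **1. The plan's own power.** Inputs from section 4.8.2: 85 or 125 evaluable subjects per active arm against 125 on placebo, log difference ln(1/0.7) = 0.3567, SD 1.0, one-sided alpha 0.05 (z = 1.645). Power = Φ(0.3567/(SD·√(1/n₁ + 1/125)) − 1.645).
- Lower doses: √(1/85 + 1/125) = 0.1406; 0.3567/0.1406 = 2.537; Φ(0.892) = 81.4%.
- 300 mg: √(2/125) = 0.1265; 0.3567/0.1265 = 2.820; Φ(1.175) = 88.0%.

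Both stated targets are met. SD 1.0 gives a coefficient of variation of √(e − 1) = 1.31, as stated.

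**2. What a second collection removes.** Let T be the between-subject variance of the true log level and s the within-subject SD of one three-void log value. One collection explains T²/(T + s²) of the outcome variance. Two collections with uncorrelated errors explain T²/(T + s²/2). Neither T nor s is in the protocol, so both are assumptions. As a guide to the upper end of T, a uniform spread of log UACR over 100 to 3000 mg/g has SD ln(30)/√12 = 0.98, a variance of 0.96.

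Example with T = 0.8 and s = 0.4: 0.64/0.96 = 0.667 and 0.64/0.88 = 0.727, a saving of 0.061. Taking SD 1.0 as the residual SD with one baseline, that is 6.1%. Over the grid, the saving in residual variance is:

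| T | s = 0.2 | s = 0.3 | s = 0.4 | s = 0.5 |
|---|---|---|---|---|
| 0.50 | 1.8% | 3.5% | 5.2% | 6.7% |
| 0.64 | 1.8% | 3.7% | 5.7% | 7.5% |
| 0.80 | 1.9% | 3.8% | 6.1% | 8.2% |
| 0.96 | 1.9% | 3.9% | 6.3% | 8.8% |

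**3. In power.** Replace SD 1.0 by √(1 − saving). From 1.8% to 8.8%, lower-dose power becomes 82.0 to 84.4% (a rise of 0.6 to 3.0 points) and 300 mg power 88.5 to 90.4%. In evaluable subjects, 505/(1 − saving) − 505 is about 9 to 49.

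**4. Sensitivity.**
- *Correlated errors.* With error correlation c, s²/2 becomes s²(1 + c)/2. At c = 0.5 the saving is 1.7 to 1.9% for s = 0.3 and 3.0 to 4.2% for s = 0.5. At s = 0.2 it is only about 0.9%, or 0.3 points of power.
- *Correlation form.* Let ρ be the correlation of baseline with Day 169 and r that between the two collections. The saving is ρ²(1 − r)/[(1 + r)(1 − ρ²)]. It runs from 0.5% (ρ 0.4, r 0.95) to 19.8% (ρ 0.8, r 0.8).
- *Meaning of SD 1.0.* The protocol does not say whether this is the SD of change or the residual SD. If it is the SD of change, residual variance with one baseline is already about 0.93 to 0.99 (T 0.6 to 0.9, s 0.3 to 0.5). Lower-dose power then starts at 81.7 to 83.9%. The rise is still about 1.2 to 3.0 points.

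**5. A check on the averaged covariate.** With equal error variances, the mean of the two log values saves as much as two covariates, but only if change is also measured from that mean. If change is taken from Day 1 and only the mean is adjusted for, the difference between Day 1 and the mean stays in the outcome and adds s²/2. At s = 0.4 that is 0.08, more than the 0.061 saved.

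**The case against.** The protocol never defines baseline UACR as Visit 2, Visit 3 or their mean. One covariate term does not imply one collection, and an averaged baseline would fit section 4.8.3.1 as worded. Deriving a baseline value is ordinary SAP content, and the SAP is not at hand. This stands: a reader might infer that the plan discards a collection, but the documents do not show that, and the missing definition is not itself a fault. The covariate list, however, is fixed in the protocol, so a second UACR covariate would depart from its text and is best settled there.

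The size is also open to challenge. No within-subject variance or correlation is given. Screening runs from Day -37 to Day -3, so the two sets may lie only days apart and their errors may be correlated. The two sets are separate, but calling them independent would go too far. This stands too, and limits the claim to its direction and a wide range.

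A last worry is that Visit 2 is the eligibility measurement, restricted in range and open to one repeat. That may reduce its information. It does not bias the comparison between arms, because the value precedes randomisation and is handled alike in every arm.

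**Conclusion.** The point holds as an optional gain in precision from data already scheduled. With a within-subject log SD of 0.2 to 0.5 and uncorrelated errors, residual variance falls by about 2 to 9%, worth roughly 0.6 to 3 points of power in the 30, 60 and 120 mg arms. At an error correlation of 0.5 and SD 0.3 to 0.5 the fall is about 2 to 4%. The wider grid spans about 0.5 to 20%. All of these rest on assumed variances; none is a property of this trial that the protocol establishes.

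Two stronger readings are not supported. One is that the trial is underpowered without the change: 81.4% and 88.0% meet the stated 80% and at least 85%. The other is that the primary model is wrong: an MMRM with baseline log UACR and its visit interaction is valid whichever collection supplies the baseline.

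**What to change.** - Define baseline for the change score as the Day 1 (Visit 3) log UACR.
- Add Visit 2 log UACR as a second continuous covariate in the MMRM and the ANCOVA, with its interaction with visit in the MMRM. Apply the same to the Day 85 analysis.
- Alternatively, use the mean of the two log values as the single covariate. In that case measure change from the same mean, for the reason in step 5 of the working.
- State before unblinding which Visit 2 value enters the model if the collection was repeated, and how a missing or incomplete set is handled, using only pre-randomisation data and the same rule in all arms.

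The cost is a sentence or two of text and no new sampling. With six post-baseline visits to Day 169 (Visits 4 to 9), the MMRM gains one main effect and five interaction parameters, which is negligible against about 505 evaluable subjects. If the SAP already averages the two collections for both the covariate and the change score, one sentence in the protocol saying so is enough.
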